3.1. Summary of ReActiv8

The Mainstay ReActiv8 is an implantable electrical stimulation system that consists of an implantable pulse generator, leads, programmer, activator and magnet. Refer to the Investigator Brochure (IB) or the Implant and Programming Manual for more detail on device specifications and operation.

Implantable Components of ReActiv8

The ReActiv8 IPG, and the ReActiv8 leads (available in either 45 cm or 65 cm lengths), plus suture sleeves, are designed for permanent implant. The implantable components of ReActiv8 are supplied sterile, and are intended for single use only.

- Model 5100 ReActiv8 Implantable Pulse Generator (“IPG”)
- Model 8000-45 ReActiv8 Percutaneous Stimulation Lead, 45 cm length (“lead”)
- Model 8000-65 ReActiv8 Percutaneous Stimulation Lead, 65 cm length (“lead”)
- Model 8145 ReActiv8 Percutaneous Stimulation Lead, 45 cm length (“lead”)
- Model 8165 ReActiv8 Percutaneous Stimulation Lead, 65 cm length (“lead”)

Note: The Model 8000-XX and Model 81XX leads are functionally equivalent. The Model 81XX leads incorporate a change to eliminate unused wires within the lead.

Non-Implantable Components of ReActiv8

The Torque Wrench and Stylet are provided to facilitate implantation of the IPG and leads. The Programmer is used to communicate with the IPG in order to program the IPG operational mode and settings, read history data from the IPG, and obtain IPG and lead status information. The Activator is used to initiate and/or suspend stimulation. The Magnet is used to enter Magnet Mode (with Magnet Mode operation determined by the programmed parameters of the IPG).

- Model 6500/65X0 ReActiv8 Programmer System (“Programmer”) – All Model 65X0 Programmers contain a Lenovo E420 Laptop computer. Model 6500 contains a “universal” set of power cords (for the UK, US, Belgium and Australia), while Model 65X0 contains one power cord that varies by the intended geography for use (e.g., Model 6530 contains a US power cord only). Mainstay provides the following components of the Model 6500/65X0 Programmer in case replacements are needed:
 - Model 6600 Lenovo E420 Laptop (“E420 Laptop”)
 - Model 6700 Medical Grade AC Adapter for the Model 6500/65X0 Programmer
 - Model 6800 Battery for the Model 6600 Lenovo E420 Laptop
 - Model 6000 ReActiv8 Programmer Wand (“Wand”)
 - Model PP00 Universal Replacement Power Cord Package with AUS, UK, USA and Belgian Power Cord
 - Model PP30 USA Replacement Power Cord Package
- Model 7500/75X0 ReActiv8 Programmer System (“Programmer”) – All Model 75X0 Programmers contain a Lenovo E440 laptop computer. Model 7500 contains a “universal” set of power cords (for the UK, US, Belgium and Australia), while Model 75X0 contains one power cord that varies by the intended geography for use (e.g., Model 7530 contains a US power cord only). Additionally, the Model 7500/75X0 Programmer contains the Model 6750 Medical Grade AC Adapter and the Model 6000

Programmer Wand (unchanged from the Model 6500/65X0). Mainstay provides the following components of the Model 7500/75X0) Programmer in case replacements are needed:

- Model 7600 Lenovo E440 Laptop (“E440 Laptop”)
- Model 6750 Medical Grade AC Adapter for the Model 7500/75X0 Programmer
- Model 7800 Battery for the Model 7600 Lenovo E420 Laptop
- Model 6000 ReActiv8 Programmer Wand (“Wand”)
- Model PP00 Universal Replacement Power Cord Package with AUS, UK, USA and Belgian Power Cord
- Model PP30 USA Replacement Power Cord Package
- Model 7000 ReActiv8 Activator (“Activator”)
- Model 4000 ReActiv8 Magnet (“Magnet”)
- Model 5500 ReActiv8 Torque Wrench – single use - (“Torque Wrench”)

Accessories Included with the ReActiv8

Mainstay supplied accessories included with the ReActiv8 are:

- Torque Wrench (supplied in the IPG package and also available as a standalone accessory)
- Suture sleeve (optional - supplied in the Lead package)
- Lead Stylet (supplied in the Lead package)
- Model TUN1 Mainstay Tunneler

Other Accessories

The Lead is designed to be placed using a commercially available 7 Fr Introducer Kit (not included with ReActiv8) and the Mainstay Model TUN1 Tunneler (included with ReActiv8) or commercially available equivalent.

The ReActiv8 delivers stimulation via electrodes placed adjacent to the medial branch of the dorsal ramus nerve at the preferred location as it crosses the L3 transverse process. The electrodes are located at the distal end of a Stimulation Lead that is connected to an implantable pulse generator (IPG) placed in a surgical pocket typically above the buttocks (in a place similar to that used in Spinal Cord Stimulation implants). Two leads are placed (one each left and right side) and connected to the IPG. The IPG is externally programmable with a Programmer. Stimulation is manually initiated by an external device (Activator) and can be stopped with the Activator or Magnet.

The leads incorporate a fixation mechanism that consists of two sets of 3 point tines – one facing forward and one facing backwards. The tines are positioned to lie on either side of the intertransversarii lateralis, thus reducing the risk of lead dislodgement by either advancement or retraction. The lead body is a polyurethane tube containing spiral wound multi-filar wires and incorporates a lumen to allow passage of a stylet.

3.2. Surgical Implantation and Device Activation

Surgical implantation is adapted from familiar techniques used for medial branch rhizotomy and spinal cord stimulation. Details of the recommended surgical procedure, device programming and use by the Subject are to be found in the Implant and Programming Manual and the User Manual.

In normal use, following implantation and a suitable recovery period, the IPG is programmed to deliver stimulation that elicits smooth contraction of the lumbar multifidus. Typical parameters

are 0.5 mA, 200 μ s, 20 Hz, with 10 seconds of stimulation followed by 20 seconds of no stimulation, delivered for a Session of 30 minutes. Refer to the Implant and Programming Manual for device programming.

To start a Session, the Subject is positioned comfortably prone or lying on the side. The Subject initiates delivery of electrical stimulation with the Activator, which can also be used to stop stimulation (e.g.: in case of interruption). Two sessions of stimulation, each of 30 minutes, are delivered each day (e.g. morning and evening).

3.3. Physician Training

All physicians who will implant any portion of the ReActiv8 in the clinical Trial will participate in product training as outlined in the Training Strategy. A “Certificate of Completion” will be issued to each implanting physician who completes the training to the satisfaction of the trainer.

All physicians and other health care personnel who will interact with the programmer (e.g.: non-implanting physicians) will receive training from the Sponsor, which includes lectures and use of a programmer with a simulator (e.g.: a ReActiv8 IPG connected to a dummy load). This training will also include interaction with the external components handled by the Subject, including the Activator and Magnet.

4. Study Design

International, multi-center, prospective, randomized, sham controlled, blinded Trial with an adaptive statistical design.

4.1. Hypothesis

In Subjects with chronic low back pain and no prior surgery and with unsatisfactory pain relief despite medical management (including at least physical therapy and medications), episodic electrical stimulation of the medial branch of the dorsal ramus nerves to cause contraction of the lumbar multifidus muscles can lead to relief of low back pain and the disabling effects of back pain.

4.2. Proposed Indications for Use for ReActiv8

ReActiv8 is an adjunct to medical management in adults with Chronic Low Back Pain for relief of pain in subjects who have failed at least medical management and physical therapy.

4.3. Study Population

Subjects with chronic low back pain that impacts their daily living, who satisfy the following general criteria:

- 1 Chronic low back pain and disability despite medical management, including at least one attempt of physical therapy treatment for low back pain (which may optionally be accomplished over multiple episodes or flare-ups of low back pain), and may be using prescribed pain relieving drugs (including muscle relaxants) which have been at a stable appropriate dose for a minimum of 30 days.
- 2 No contraindications for enrollment.

Detailed Inclusion and Exclusion criteria are listed in Section 5.

4.4. Study Size and Duration

A minimum of 116 evaluable Subjects is required to sufficiently power the primary endpoint. To allow for attrition, 128 Subjects will be randomized as part of the Intent to Treat Cohort. Up to 80 additional Subjects will be randomized as part of the Surgical Roll In phase as described below (assuming one implanting surgeon per site). Therefore, the total number of implanted and randomized Subjects will be up to 208. In order to account for screen failures prior to implant up to 800 Subjects will be enrolled. An adaptive statistical design using a single interim look will be used for sample size re-estimation.

4.4.1. Investigational Sites

Investigators may include a number of different specialties including Physical Medicine and Rehabilitation (PM&R), Interventional Pain, Neurosurgery, Neurology and Spine Surgeons. The key investigational activities include Subject recruitment, device implant, and Subject follow up (including device management and Trial data collection). Some investigators will perform all of these activities, and some may not. For example, some PM&R physicians will not perform

surgery, and the surgery will be performed by a Sub-investigator (e.g.: a neurosurgeon) who may be at a different site. The Trial design accommodates this situation.

There will be up to 40 investigational sites with a Principal Investigator who may or may not be the implanting physician. One or more Sub-investigators per site (or affiliated site if the affiliated site has a different Ethics Committee or IRB) may be used for example for device implantation and Subject recruitment.

4.4.2. Surgical Roll In Phase

Following training, up to the first two Subjects implanted by the same implanting physician may be prospectively included in a Surgical Roll In group and not included in the Intention To Treat Cohort. The Surgical Roll In phase for each implanting physician will be deemed complete upon consultation with the implanting physician and the Sponsor. In some cases, there will be no Surgical Roll In phase, for example if the implanting physician participated in the ReActiv8-A Trial. Note that Subjects included in the Surgical Roll In Phase who are not successfully implanted are not included in the Surgical Roll In group.

All Subjects implanted in the Surgical Roll In group will be randomized to either Treatment or Control, and follow the identical visit schedule as Subjects included after the Surgical Roll In phase. With approximately 40 implanting physicians and up to 2 Subjects in the Surgical Roll In phase per implanting physician, up to 80 Subjects may be included in the Surgical Roll In group.

4.4.3. Study Duration

Total study duration is anticipated to be ≤60 months from first Subject Baseline Visit through PMA submission.

Informed consent for all Subjects will allow for continuing data collection for a total period of 7 years from Baseline Visit.

4.5. Assessment of Lumbar Multifidus Dysfunction

The Prone Instability Test (PIT) has been utilized in variety of studies⁵⁵ and is used in this Trial to identify Subjects likely to have multifidus dysfunction. The PIT was designed to identify Subjects who would likely respond to a lumbar stabilization exercise program, and in many of these Subjects spine instability is thought to be due to LM dysfunction consequent to compromised neural drive to the LM. It has established reliability ($K = 0.87$).⁵⁶ It was one of 4 variables shown to be predictive of success with a stabilization exercise program for Subjects with low back pain that included exercises designed to reactivate the LM.⁵⁷ Additionally, the same study demonstrated that those Subjects who had a positive PIT also had reduced LM thickness change when compared to Subjects who had a negative PIT. The PIT may be the only predictive test that has demonstrated reasonable inter-tester reliability.⁵⁸

The PIT will be performed by appropriately qualified individuals (e.g.: physical therapist, Physical Medicine and Rehabilitation Physician, Orthopedic Surgeon). Each person performing the PIT shall undergo training as follows:

- The training materials shall be standardized across sites.
- The person conducting the training shall be a reputable and appropriately qualified individual with experience in training on the PIT (e.g.: a physical therapist or physical medicine physician who regularly conducts training of other specialists).

- A formal training plan shall be developed in conjunction with the trainer(s), including “hands on” conduct of the PIT.
- Each trainee will be assessed by the trainer, including a “hands-on” demonstration of competence in performing the PIT to validate the training.
- Upon successful completion of the training and assessment, the trainer shall sign a “Certificate of Training” for the trainee to document that the trainee is qualified to conduct the PIT for this Trial.

In summary, to conduct the PIT, the Subject is positioned prone on an examination table. The test is conducted in two stages:

Stage 1: Tester performs Posterior-Anterior (P-A) glides over each lumbar segment for pain provocation and identifies the painful segments.

Stage 2: Repeat P-A with hips extended (Feet just off of the floor) as shown in Figure 1.

A Positive Test is when any previously painful segments become pain-free. The level of instability will be documented.

Figure 1: Conducting the Prone Instability Test

4.6. Outcome Measures

Several outcome measures are used to assess the primary and secondary endpoints of the Trial.

4.6.1. Low Back Pain Visual Analog Scale (VAS)

The primary outcome measure is pain, a Patient Reported Outcome (PRO). The instrument used for evaluating pain is the continuous Visual Analog Scale comprised of a horizontal line 10cm in length, anchored by 2 verbal descriptors, one for each symptom extreme for Low Back Pain, as recommended by IMMPACT.⁴⁴

Subjects will be advised to place a line on the VAS that represents their average low back pain for the last 7 days. The scale is anchored with “no pain” on the left side of the scale to “worst imaginable pain” on the right side of the scale.

Note: This is a study on *low back pain*. Thus the Subject will be presented a VAS that is specific to the low back pain that led to being enrolled in this study. This allows separation of the low back pain symptoms from other pain causing events (e.g.: toothache) which could confuse interpretation of the results. People with low back pain often also report leg pain, which should be distinguished from the low back pain that led to enrollment in the Trial.

The VAS for low back pain is recorded by the Subject at each of the visits and is used for the primary outcome.

A daily Journal will also be collected for 7 days prior to each visit through the 120 day follow-up, completed preferably at the same time of day (e.g.: between 5PM and 8PM).

4.6.2. ODI

Oswestry Disability Index (ODI) is a disease specific assessment of the disabling effects of back pain.⁴⁸ The ODI covers 1 item on pain and 9 items on activities of daily living (personal care, lifting, walking, sitting, standing, sleeping, sex life, social life, and traveling). ODI is reported as a score from 0 to 100%.

The relevance of changes in ODI has been explored by many authors, and discussions abound on Minimal Clinically Important Difference (MCID), Minimally Important Change (MIC) and the like. It is important to distinguish between significance of change scores for studies on *acute* low back pain where the natural history of improvement would suggest reversion to the mean, and studies on chronic low back pain where the likelihood of improvement is low. Hägg et al⁵⁹ suggested that an absolute change of 10 (in the 100 point ODI scale) is the MCID and Ostelo⁶⁰ concurs that a Minimally Important Change is 10.

4.6.3. EQ-5D

EQ-5D is the acronym for the European Quality of Life Score on Five Dimensions. There are many instruments used for assessment of Quality of Life,⁶¹ and EQ-5D appears to be the most commonly used in studies of therapies for back pain, and is often used for cost utility assessment.⁶² The EQ-5D descriptive system comprises the following 5 dimensions: mobility, self-care, usual activities, pain/discomfort and anxiety/depression. The original EQ-5D used a 3 level reporting system (no problems, some problems, extreme problems), and more recently a five level reporting system has been developed and validated (no problems, slight problems, moderate problems, severe problems, and extreme problems), referred to as the EQ-5D-5L, which has been tested and validated.^{63,64} This Clinical Investigation uses the EQ-5D-5L, referred to in its short form as EQ-5D.

The EQ-5D is designed for use primarily as a self-reported measure (i.e.: the questionnaire is completed by the Subject alone), and therefore lends itself to clinical trials in which the outcome assessment is to be blinded. Population norms for EQ-5D for various populations have been reported, and categorized by age, gender and social class. EQ-5D is reported as an index up to 1.00 (note: EQ-5D index scores of <0 are possible in some circumstances).

4.6.4. Percent Pain Relief (PPR)

Percent Pain Relief (PPR) is a question asked to the Subject by the Investigator or Coordinator in which the Subject is asked to report the percent pain relief at the time of the current visit compared to the pain at baseline.

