4.7.2. Secondary Efficacy Endpoints

All tests of significance will be tested utilizing an overall Type I error of 5%. The overall Type I error will be maintained by utilizing Hochberg's method to test the collection of the first five secondary objectives. These will be tested only if the primary efficacy endpoint is met.

1. Comparison of change from baseline in Oswestry Disability Index (ODI) between Treatment and Control groups at the Primary Endpoint Assessment Visit.
2. Comparison of change from baseline in EQ-5D between Treatment and Control groups at the Primary Endpoint Assessment Visit
3. Comparison of Percent Pain Relief between Treatment and Control groups reported by the Subject at the Primary Endpoint Assessment Visit
4. Comparison of Subject Global Impression of Change at the Primary Endpoint Assessment Visit
5. Comparison of number of Subjects with Resolution of Low Back Pain (remitters or cure, defined as a VAS score ≤ 2.5 cm) at the Primary Endpoint Assessment Visit
6. Evaluation of changes in primary and secondary efficacy metrics in the Crossover Group (as defined in Section 4.10) following the Outcome Post Crossover Visit.

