4.11. Data Collection

To avoid introduction of bias, all Subject reported endpoint data at Subject contact visits will be collected before any other intervention or interview during the Subject follow up. The data collection session shall not be attended by people not necessary for the data collection (e.g.: Investigator, the Subject's relatives or friends, or Sponsor personnel).

Programming the ReActiv8 and data collection via the Physician Programmer will be performed by the Investigator or delegate, with the assistance (if requested) of personnel from the Sponsor or CRO under Investigator direction and guidance.

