9.1.11. Subject Global Impression of Change

Subject Global Impression of Change consists of the questionnaire as detailed in 4.6.5.

Collection method: Subject completes a paper form and results are transferred to paper CRF or eCRF

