8.6.3. SEE 3: Percent Pain Relief

The secondary Percent Pain Relief efficacy objective will be tested under the following hypotheses:

$$H_0: \mu PPR_T = \mu PPR_C$$

$$H_A: \mu PPR_T \neq \mu PPR_C$$

Where μPPR_T is the mean percent pain relief in the Treatment group and μPPR_C is the mean percent pain relief in the Control group at the Primary Endpoint Assessment Visit. The hypotheses will be tested using a two-sided two-sample t-test for a difference in mean changes.

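### Percent Pain Relief, a formally tested secondary, may be asked by the Investigator, whom Protocol 4.11 treats as unnecessary when subject-reported data are collected; the other four tested secondaries rest on self-completed forms

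*Protocol*

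**What the plan says.** **Collection of PPR.** Protocol 4.6.4 states that PPR "is a question asked to the Subject by the Investigator or Coordinator". Protocol 9.1, which sets out collection methods instrument by instrument, has no PPR entry, so 4.6.4 is the only instruction.

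**Status of PPR.** Protocol 4.7.2 lists as its third secondary endpoint: "Comparison of Percent Pain Relief between Treatment and Control groups reported by the Subject at the Primary Endpoint Assessment Visit". It uses "Hochberg's method to test the collection of the first five secondary objectives", and only if the primary endpoint is met. For PPR, SAP 8.6.3 adds: "The hypotheses will be tested using a two-sided two-sample t-test for a difference in mean changes".

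**Rule for subject-reported data.** Protocol 4.11, whose stated aim is to avoid bias, requires that "all Subject reported endpoint data at Subject contact visits will be collected before any other intervention or interview during the Subject follow up". It adds that the session "shall not be attended by people not necessary for the data collection (e.g.: Investigator" is the first example given, followed by family, friends and Sponsor staff.

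**The other tested secondaries.** ODI is filled in by the Subject alone (9.1.7). VAS, which defines resolution of back pain, is completed unaided (9.1.8). EQ-5D is a paper form filled in by the Subject (9.1.13). SGIC has the instruction "Collection method: Subject completes a paper form and results are transferred to paper CRF or eCRF" (9.1.11).

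**Safeguards.** Protocol 4.9 lists Investigators as blinded, requires anyone carrying out an interview-based assessment to be blinded, calls for scripted interaction at follow-up visits, and tells Subjects not to disclose what they feel.

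**The concern.** The protocol itself treats the absence of an assessor as a protection: 4.9 regards the primary VAS as inherently blinded for that reason, and 4.6.3 commends EQ-5D because the Subject fills it in alone. PPR is the one tested secondary without that protection, and 4.6.4 allows it to be asked by the very role that 4.11 names as unnecessary.

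An answer given to a member of the site team can be coloured by courtesy or by what either party expects. If that colouring is the same in both arms, it adds noise. If the asker knows or suspects the allocation, it can differ by arm and appear as a treatment effect. At stake is the credibility of one formally tested secondary result.

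**Working it through.** **1. Is there a conflict?** Protocol 4.6.4 permits two askers. Section 4.11 names the Investigator as someone not needed and does not name the Coordinator. The direct conflict is therefore with the Investigator option. A site that always uses the Coordinator satisfies both sections.

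**2. Does the blinding rule close the gap?** Four places bear on this:
- Protocol 4.9 requires blinded interviewers, but accepts that managing an adverse event may unblind an Investigator.
- Protocol 4.11 assigns programming to the Investigator or a delegate.
- Protocol 6.4 has the two arms programmed differently at Visit 4.
- Protocol 6.5 to 6.7 list threshold testing and adjustment at Visits 5 to 7 for the Treatment group only.

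Whoever carries out those tasks can infer the arm. No section says that this person may not ask PPR at Visit 7 or Visit 8. Collecting the data first at each visit does not help, because the knowledge would come from earlier visits.

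**3. Sample size for the illustration.** Protocol 4.7.1.2 gives 116 evaluable Subjects (responder rates 50% and 25%, power 80%, two-sided 5%). To reproduce it, with a mean rate of 0.375:

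n per arm = [1.960 × √(2 × 0.375 × 0.625) + 0.842 × √(0.50 × 0.50 + 0.25 × 0.75)]² / 0.25² = (1.342 + 0.557)² / 0.0625 = 57.7, rounded up to 58, or 116 in total. The figure reproduces.

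**4. What an asker effect would do.** The documents give neither an SD for PPR nor an asker effect, so both are assumed. Take 58 per arm, no true effect and a shift *b* points in favour of Treatment. By normal approximation:
- SE = SD × √(2/58) = SD × 0.1857, and δ = *b*/SE.
- Two-sided rejection = 1 − Φ(z − δ) + Φ(−z − δ), with z = 1.960 at 0.05 or 2.576 at 0.01.

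Example with SD 30 and *b* = 5: SE = 5.57 and δ = 0.898. At 0.05, 0.144 + 0.002 = 0.146. At 0.01, 0.047.

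| Assumed SD | 3-point shift (0.05 / 0.01) | 5-point shift (0.05 / 0.01) | 10-point shift (0.05 / 0.01) |
|---|---|---|---|
| 25 | 9.9% / 2.7% | 19.0% / 6.7% | 57.7% / 33.7% |
| 30 | 8.4% / 2.2% | 14.6% / 4.7% | 43.5% / 21.7% |
| 35 | 7.5% / 1.8% | 12.0% / 3.6% | 33.7% / 15.0% |

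With no shift the formula returns 5% and 1%.

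**5. Why two levels.** Hochberg's thresholds for five tests are 0.05, 0.025, 0.0167, 0.0125 and 0.01. A PPR p-value just under 0.05 counts only if all five p-values are at or below 0.05. One at or below 0.01 counts whatever the others show. The two columns are therefore the most lenient and the strictest level at which PPR could be judged.

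**The case against.** The strongest reply is that the protocol foresaw interview items and protected them. Section 4.9 demands blinded interviewers and scripted contact, and 4.11 and Section 6 put data collection first. The person who must ask a question is arguably necessary for collecting the answer, and the Coordinator may do it. Programming may be delegated, and 10.7 says that unblinded Sponsor representatives may be involved in it. If an Investigator who programs learns the arm, that is a general blinding weakness that touches the investigator-rated Clinical Global Impression at least as much. Finally, 4.9 expects Treatment Subjects to be predominantly unblinded and the Control group about half unblinded, so a paper form would still carry the Subject's own expectations.

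Most of this stands, and it limits the point. What remains is that delegation is optional, that the blinding rule is not backed by any separation between programming and asking PPR, and that the asker's contribution can be removed even though the Subject's cannot.

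A reader might infer more than the documents support:
- *That the Investigator is excluded from all data collection.* Section 4.11 concerns subject-reported data; it also has the Investigator or a delegate collect programmer data, and the Investigator completes the Clinical Global Impression (9.1.12).
- *That PPR is the only endpoint item asked by staff.* The Coordinator also asks about medication use, a component of the primary endpoint (9.1.9), although that is not a rating.
- *That the answer must be spoken.* Section 4.6.4 says the question is asked; a spoken reply is the natural reading, but it is not stated.
- *That a labelled claim hangs on PPR.* Neither document says so.

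**Conclusion.** The point holds as an inconsistency and an avoidable weakness in a gated secondary endpoint. The conflict between 4.6.4 and 4.11 covers the Investigator option only. The 4.9 safeguards reduce the risk of bias that differs by arm but do not remove it, because the Investigator may program the arms or be unblinded and is still allowed to ask PPR. The self-completed VAS in the primary endpoint is unaffected.

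The size is unknown. For an assumed 5-point shift and an assumed SD of 25 to 35, the PPR test would reject about 12% to 19% of the time at 0.05 and about 4% to 7% at 0.01. These figures also assume 58 analysed per arm, although the SAP names more than one population for the secondaries (7.2, 8.2, 8.6). A reader might take them as the trial's false-positive rate. They are not: they describe the PPR test alone, ignore its dependence on the other tests, and matter only once the primary is met. Nothing in the documents shows that a shift of this size would occur.

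**What to change.** Amend Protocol 4.6.4 so that the Subject writes PPR alone on the paper form, together with VAS and SGIC and before any device activity. Add a PPR entry with that collection method to 9.1.

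If an interview is kept, the minimum is to delete the Investigator from 4.6.4 and require a blinded asker who has no programming role.

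The preferred change costs one line on an existing form and leaves the visits, sample size and analysis as they are. It removes the asker's influence; expectation bias among Subjects who guess their arm would remain.
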